8.3 Lost to Follow Up

If a participant fails to return to the clinic for a required study visit and/or if the site is unable to contact the participant, the following procedures are to be performed:

- The site must attempt to contact the participant and reschedule the missed visit. If the participant is contacted, the participant should be counseled on the importance of maintaining the protocol-specified visit schedule.
- The investigator or designee must make every effort to regain contact with the participant at each missed visit (eg, phone calls and/or a certified letter to the participant's last known mailing address or locally equivalent methods). These contact attempts should be documented in the participant's medical record.

9. Study Assessments and Procedures

- Study procedures and their timing are summarized in the SoA.
- Adherence to the study design requirements, including those specified in the SoA, is essential and required for study conduct.
- The Investigator is responsible for assuring that procedures are conducted by appropriately qualified or trained staff. Delegation of study site personnel responsibilities will be documented in the Investigator Trial File Binder (or equivalent).
- All screening evaluations must be completed and reviewed to confirm that potential participants meet all eligibility criteria. The investigator will maintain a screening log to record details of all participants screened and to confirm eligibility or record reasons for screening failure, as applicable.
- Procedures conducted as part of the participant's routine clinical management (eg, blood count) and obtained before signing of ICF may be utilized for screening or baseline purposes provided the procedure met the protocol-specified criteria and were performed within the time frame defined in the SoA.

- Additional evaluations/testing may be deemed necessary by the investigator and or the Sponsor for reasons related to participant safety. In some cases, such evaluation/testing may be potentially sensitive in nature (eg, HIV, Hepatitis C, etc.), and thus local regulations may require that additional informed consent, and assent if applicable, be obtained from the participant. In these cases, such evaluations/testing will be performed in accordance with those regulations.

The maximum amount of blood collected from each participant to assess the primary study objective over the duration of the study, including any extra assessments that may be required, will not exceed 14 mL.

Repeat or unscheduled samples may be taken for safety reasons or for technical issues with the samples.

9.1 Administrative and General Procedures

9.1.1 Informed Consent/Assent

The investigator or qualified designee must obtain documented consent, and assent if applicable, from each potential participant or each participant's legally acceptable representative prior to participating in a clinical study-. If there are changes to the participant's status during the study (eg, health or age of majority requirements), the investigator or qualified designee must ensure the appropriate consent/assent is in place.

9.1.1.1 General Informed Consent/Assent

Consent/assent must be documented by the participant's dated signature or by the participant's legally acceptable representative's dated signature on a consent/assent form along with the dated signature of the person conducting the consent discussion.

A copy of the signed and dated consent/assent form should be given to the participant before participation in the study.

The initial informed consent/assent form, any subsequent revised written informed consent/assent form and any written information provided to the participant must receive the IRB/IEC's approval/favorable opinion in advance of use. The participant or his/her legally acceptable representative should be informed in a timely manner if new information becomes available that may be relevant to the participant's willingness to continue participation in the study. The communication of this information will be provided and documented via a revised consent/assent form or addendum to the original consent/assent form that captures the participant's dated signature or by the participant's legally acceptable representative's dated signature.

Specifics about a study and the study population will be added to the consent/assent form template at the protocol level.

The informed consent will adhere to IRB/IEC requirements, applicable laws and regulations and Sponsor requirements. The assent, as applicable will adhere to IRB/IEC requirements, applicable laws and regulations and Sponsor requirements.

9.1.2 Inclusion/Exclusion Criteria

All inclusion and exclusion criteria will be reviewed by the investigator or medically qualified designee to ensure that the participant qualifies for the study.

9.1.3 Participant Identification Card

All participants will be given a Participant Identification Card identifying them as participants in a research study. The card will contain study site contact information (including direct telephone numbers) to be utilized in the event of an emergency. The investigator or qualified designee will provide the participant with a Participant Identification Card immediately after the participant provides written informed consent/assent. At the time of treatment allocation/randomization, site personnel will add the treatment/randomization number to the Participant Identification Card.

The participant identification card also contains contact information for the emergency unblinding call center so that a health care provider can obtain information about study treatment in emergency situations where the investigator is not available.

9.1.4 Medical History

At the Day 1 visit, the participant's medical history for the year prior to Day 1 will be collected. For participants in the 16- to 26-year-old women's group, lifetime gynecological history will also be collected at the Day 1 visit. For participants in the 16- to 26-year-old men's group, lifetime genitourinary history will also be collected at the Day 1 visit.

After the Day 1 visit, any new medical history that has not been previously documented (either as adverse experiences or as medical history conditions) will be collected. For participants in the 16- to 26-year-old women's group, new gynecologic history will be collected. For participants in the 16- to 26-year-old men's group, new genitourinary history will be collected.

Other documentation, such as demographics, sexual history, pregnancy history, and contraceptive use, will be collected in the data collection system, as discussed in the electronic case report form (eCRF) entry guidelines.

9.1.5 Prior and Concomitant Medications Review

9.1.5.1 Prior Medications

Prior and concomitant use of medicines and nonstudy vaccines should be documented in the data collection system in the following manner:

1. "Special medications" (corticosteroids, immunosuppressives, immune globulins, and blood products) from 3 days prior to Day 1 through Month 7.
2. "Other medications" from 3 days prior to each study vaccination through 14 days after each study vaccination
3. "Nonstudy inactive or recombinant vaccines" for 14 days prior to each study vaccination through 14 days after each study vaccination

4. “Non-study live vaccines” for 21 days prior to each study vaccination through 14 days after each study vaccination.

9.1.5.2 Concomitant Medications

The investigator or qualified designee will record medication, if any, taken by the participant during the study as outlined above.

9.1.6 Assignment of Screening Number

All consented participants will be given a unique screening number that will be used to identify the participant for all procedures that occur prior to treatment allocation. Each participant will be assigned only one screening number. Screening numbers must not be re-used for different participants.

Any participant who is screened multiple times will retain the original screening number assigned at the initial screening visit.

9.1.7 Assignment of Treatment/Randomization Number

All eligible participants will be allocated, by non-random assignment, and will receive a treatment/randomization number. The treatment/randomization number identifies the participant for all procedures occurring after treatment allocation/randomization. Treatment allocation will occur centrally using an IRT system. All prevaccination (screening) data must be collected and all study procedures must be completed before the participant is assigned a treatment/ randomization number and vaccine administration.

Day 1 (and all Day 1 procedures) must occur within 14 days after informed consent (screening). Once a treatment/randomization number is assigned to a participant, it can never be re-assigned to another participant.

A single participant cannot be assigned more than 1 treatment/randomization number.

9.1.8 Treatment Administration

Vaccine will be administered at the study sites by the investigator and/or study staff.

The first dose of study vaccine will be administered on Day 1, which should be the day of allocation. The second and third (final) doses of study vaccine will be administered subsequently, at time points 2 and 6 months, respectively, after the first dose.

Participants should not be enrolled or vaccinated if protocol requirements are not met. At Day 1, vaccine should be administered after the blood draw for HPV testing (see Section 9.2.1 for procedures related to blood draw). Pregnant participants should not be vaccinated (see Section 9.5.2 for management of study visits and study vaccinations for pregnant participants). Section 9.10.1 provides additional information on other prerequisites for vaccination visits.

9.1.8.1 Preparation of Study Vaccine for Administration

This study vaccine must be used as supplied (no dilution before administration). Prior to administration, mix the contents of the vial thoroughly by rolling the vial between the palms of both hands for 30 seconds. Withdraw a 0.5-mL dose from the vial, which contains approximately 0.75 mL of study vaccine. The study vaccine should be a whitish, semi-translucent suspension when thoroughly mixed. If the appearance is otherwise, do not administer and contact the Sponsor immediately.

9.1.8.2 Study Vaccine Administration

Study vaccine will be administered at Day 1, Month 2, and Month 6. At each vaccination visit, participants will receive 9vHPV vaccine as a 0.5-mL intramuscular injection. The deltoid muscle of the nondominant arm is the preferred site of vaccination.

Study vaccinations should not be administered in the buttocks area. If the female participant has an implanted contraceptive (eg, NORPLANT™) at the time of the study vaccination, avoid administering the study vaccination in the arm with the implanted contraceptive. If female participants have received injectable contraceptives (eg, DEPO PROVERA™) or implanted contraceptives (eg, NORPLANT™) in both arms in the past 9 months, the injection may be given in the thigh rather than in an arm. Injections should not be given within 2 cm of a tattoo, scar, or skin deformation.

Injections should be administered at a 90° angle into the muscle tissue using a needle long enough to ensure intramuscular deposition of study vaccine. The study vaccine should be administered in the deltoid muscle using preferably a 1.0-mL syringe (the largest allowable size is a 3.0-mL syringe) with the following needle length and gauge specifications:

- 1-inch needle, 22 to 23 gauge for participants weighing <200 pounds (<90.9 kg)
- 1½-inch needle, 22 to 23 gauge for participants weighing ≥200 pounds (≥90.9 kg)
- 1½ -inch needle, 22 to 23 gauge for thigh injections

All participants will be observed for at least 30 minutes after each study vaccination for any untoward effects, including allergic reactions. This observation period will be documented in the participant's study chart.

9.1.8.3 Timing of Dose Administration

Vaccination will be administered at the following time points: Day 1, Month 2, and Month 6.

Acceptable day ranges for vaccination visits are as follows:

- Dose 1: Day 1 (±0 days)
- Dose 2: Month 2 (±3 weeks)
- Dose 3: Month 6 (±4 weeks)

The Day 1 visit is defined as the day that the first study vaccination is given (ie, date when Dose 1 of 9vHPV vaccine is injected).

The visit windows described here are for site scheduling purposes. The visit windows used for exclusion from the statistical analyses are provided in Section 10.5.1.

For post-Day 1 vaccinations, the day ranges for inclusion in the statistical analysis are wider than the protocol specified visit windows primarily to account for differences at the sites in counting months (eg, 1 calendar month versus 30 days versus 4 weeks).

To calculate visit windows, assume 1 month equals 30 days and 1 week equals 7 days.

9.1.9 Discontinuation and Withdrawal

Participants who discontinue study treatment prior to completion of the vaccination regimen should be encouraged to continue to be followed for all remaining study visits.

When a participant withdraws from participation in the study, all applicable activities scheduled for the final study visit (exception: serum collection should not be done if the participant has not received all 3 scheduled doses of study vaccine) should be performed (at the time of withdrawal). Any adverse events which are present at the time of withdrawal should be followed in accordance with the safety requirements outlined in Section 9.3.

9.1.10 Participant Blinding/Unblinding

This is an open label study; there is no blinding for this study.

9.1.11 Calibration of Critical Equipment

The investigator or qualified designee has the responsibility to ensure that any critical device or instrument used for a clinical evaluation/test during a clinical study that provides important information about inclusion/exclusion criteria and/or safety or efficacy parameters shall be suitably calibrated and maintained to ensure that the data obtained is reliable and/or reproducible. Documentation of equipment calibration must be retained as source documentation at the study site.

Critical Equipment for this study includes:

- Refrigerator equipped with an appropriate temperature monitoring device to ensure the temperature is maintained at 2°C to 8°C for storage of study vaccine supplies
- Non frost-free freezer with an appropriate temperature monitoring device to ensure serum samples are stored at -20°C or colder until shipped to the Central Laboratory
- Centrifuge for processing of blood samples

9.1.12 Other Assessments

9.1.12.1 Physical Examination and Vital Signs Prior to Study Vaccination

A physical examination at Day 1 is optional. It will be conducted, per investigator's discretion, if needed to determine whether the subject meets enrollment criteria for the study. Physical examination details will be documented in the subject's chart and any medical condition will be documented in the data collection system.

Oral temperature, height, weight will be taken before study vaccine is administered at Day 1.

Oral temperature will also be taken before study vaccine is administered at Month 2, and Month 6 visits). If the participant has a fever (defined as an oral temperature of $\geq 100.0^{\circ}\text{F}$ or $\geq 37.8^{\circ}\text{C}$) within the 24-hour period prior to receiving a study vaccination, the participant should not receive the study vaccine, and the vaccination visit should be rescheduled until after the fever has resolved.

9.1.12.2 Optional Testing for Sexually Transmitted Infections (STIs)

Local laboratory testing to screen for sexually transmitted infections (STIs), including HPV testing (cervical and/or anal); Pap test and/or HPV polymerase chain reaction, chlamydia, gonorrhea, herpes simplex virus, syphilis, hepatitis B, and HIV may be performed on any participant at any visit if deemed necessary by the investigator. Any participant who tests positive for an STI will not be discontinued from the trial and may participate in all study procedures. These participants will be referred for appropriate counseling and treatment outside of the context of the protocol.

9.2 Efficacy Assessments

9.2.1 Serum for Anti-HPV Antibody Testing

Sample collection, storage, and shipment instructions for serum samples will be provided in the Laboratory Manual.

Each participant will have serum collected for anti-HPV measurements at scheduled time points (Section 2: SoA). For collection of the serum samples, the study sites must adhere to the procedures described in the protocol, must follow instructions provided by the Sponsor-designated Central Laboratory, and must use the materials provided by the Sponsor-designated Central Laboratory. Samples should be shipped, labeled, and handled as instructed by the Sponsor/Central Laboratory. Specimen collection supplies provided by the Sponsor/Central Laboratory must be used by the site without substitution.

The following are the step-by-step procedures for collection of study specimens, a description of supplies needed, and the guidelines for handling specimens:

- For each visit that requires a serum specimen for anti-HPV measurements, a 7-mL (non-heparinized, non-serum separator, red-top tube provided by the Sponsor-designated Central Laboratory) blood specimen will be collected and should be separated to avoid hemolysis.
- A minimum of 2.0 mL of serum should be aliquoted to a vial provided by the Sponsor-designated Central Laboratory.
- An additional approximately 0.8 mL of serum (“Retention Serum”) should be aliquoted to a vial provided by the Sponsor-designated Central Laboratory and labeled with the “Retention Serum” label provided by the Sponsor-designated Central Laboratory.
- After the serum has been processed, transfer the vials to the freezer (-20°C or lower) without delay.

- All serum samples are kept in the freezer until they shipped on dry ice as instructed by the Sponsor (see Administrative Binder).
 - If the samples thaw, contact the Sponsor.
 - Thawed serum samples require written documentation, including details such as treatment/randomization number, visit interval, date of collection, and sample accession numbers (see the Administrative Binder for a summary of deviations that require documentation in this study).
- “Serum” vials will be stored at the site at -20 °C (or lower) until shipped on dry ice to the address noted on Sponsor-designated Central Laboratory contact information page.
 - The freezer used to store the vials must be a non-frost-free freezer.
- All available serum should be used for conducting assays specified in the clinical protocol.
- “Retention Serum” vials will remain stored at the site at -20 °C (or lower).
 - The freezer used to store the vials must be a non-frost-free freezer.
- The site should ship "Retention Serum" separately from the "Serum" sample.
 - If "Retention Serum" is sent to the Sponsor-designated Central Laboratory, it may also be used for further HPV immunologic testing, in addition to tests specified in the protocol.

9.2.2 Immunogenicity Measurements

The 9-valent HPV competitive Luminex immunoassay (HPV-9 cLIA) is used for the primary and secondary objectives of the study.

The purpose of the HPV-9 cLIA assay is to quantify the antibodies specific to the neutralizing epitopes of HPV Types 6, 11, 16, 18, 31, 33, 45, 52, and 58. This assay is used by the Testing Laboratory to evaluate the serological response before and after vaccination with the 9vHPV vaccine and to measure HPV infection-induced antibodies for sero-epidemiology studies.

HPV virus-like particles (VLPs) derived from yeast for each of the 9HPV types are coupled to one of 9 distinct fluorescent Luminex MagPlex[®] magnetic microspheres. Each microsphere has its own distinct fluorescent dye that can be recognized by excitation with an infrared laser, allowing for the measurement of antibodies against multiple HPV types from a single test of a human serum sample. HPV type-specific neutralizing monoclonal antibodies conjugated with phycoerythrin (PE-mAb conjugate) compete with the antibodies in the serum sample for binding to the neutralizing epitopes of the VLPs coupled to the microspheres. After incubation with PE-mAb conjugate and sample serum, the microspheres are washed and the fluorescent signal from the PE-mAb conjugate is read. The fluorescence signal is inversely proportional to the HPV antibody concentration of the serum sample tested. Antibody concentrations are derived from a standard curve, which is generated using a Reference Standard made from a pool of serum from individuals immunized against the nine HPV types. A standard curve for each HPV type is calculated using a weighted 4-

parameter logistic curve fit. Antibody concentration results are expressed as milliMerck Units/mL (mMU/mL).

The high, medium, low, and negative controls used for this assay were collected from humans who were either HPV-seronegative, had low antibody titers from natural infection, or had medium-to-high antibody titers to the 9 HPV types following vaccination.

9.3 Adverse Events (AE), Serious Adverse Events (SAE) and Other Reportable Safety Events

The definitions of an adverse event (AE) or serious adverse event (SAE), as well as the method of recording, evaluating, and assessing causality of AE and SAE and the procedures for completing and transmitting AE, SAE and other reportable safety event reports can be found in Section 12.2 (Appendix 2: Adverse Events: Definitions and Procedures for Recording, Evaluating, Follow-up, and Reporting).

AE, SAEs, and other reportable safety events will be reported by the participant (or, when appropriate, by a caregiver, surrogate, or the participant's legally authorized representative).

The investigator, who is a qualified physician, and any designees are responsible for detecting, assessing, documenting, and reporting events that meet the definition of an AE or SAE as well as other reportable safety events. Investigators remain responsible for following up AE, SAEs and other reportable safety events for outcome according to Section 9.3.3.

9.3.1 Time Period and Frequency for Collecting AE, SAE and Other Reportable Safety Event Information

All AEs, SAEs and other reportable safety events that occur after the consent form is signed but before allocation/randomization must be reported by the investigator if they cause the participant to be excluded from the study, or are the result of a protocol-specified intervention, including but not limited to washout or discontinuation of usual therapy, diet, placebo treatment or a procedure.

From the time of allocation/randomization through 14 days following the first vaccination(s) and from the time of any subsequent vaccination(s) through 14 days thereafter, all AEs, SAEs and other reportable safety events must be reported by the investigator.

Additionally, any SAE brought to the attention of an investigator at any time outside of the time period specified in the previous paragraph also must be reported immediately to the Sponsor if the event is either:

1. A death that occurs prior to the participant completing the study, but outside the time period specified in the previous paragraph.
2. An SAE is an AE that is considered by an investigator who is a qualified physician to be vaccine related.

Investigators are not obligated to actively seek AE or SAE or other reportable safety events in former study participants. However, if the investigator learns of any SAE, including a death, at any time after a participant has been discharged from the study, and he/she considers the event to be reasonably related to the study treatment or study participation, the investigator must promptly notify the sponsor.

All initial and follow-up AEs, SAEs and other reportable safety events will be recorded and reported to the sponsor or designee within the timeframes as indicated in [Table 2](#).

Table 2 Reporting Time Periods and Timeframes for Adverse Events and Other Reportable Safety Events

Type of Event	Reporting Time Period: Consent to Randomization/ Allocation	Reporting Time Period: Randomization/ Allocation through Protocol-Specified Follow-up Period	Reporting Time Period: After the Protocol Specified Follow-up Period	Timeframe to Report Event and Follow-up Information to SPONSOR:
Non-Serious Adverse Event (NSAE)	Report if: - due to protocol-specified intervention - causes exclusion - participant is receiving placebo run-in or other run-in treatment	Report all	Not required	Per data entry guidelines
Serious Adverse Event (SAE)	Report if: - due to protocol-specified intervention - causes exclusion	Report all	Report if: - drug/vaccine related. - any death until participant completion of study (Follow ongoing to outcome)	Within 24 hours of learning of event
Pregnancy/Lactation Exposure	Report if: - due to intervention - causes exclusion	Report all	Previously reported – Follow to completion/termination; report outcome (if the participant received at least 1 vaccine dose and became pregnant)	Within 24 hours of learning of event
Cancer	Report if: - due to intervention - causes exclusion	Report all	Not required	Within 5 calendar days of learning of event
Overdose	-	Report all	Not required	Within 5 calendar days of learning of event

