5.1 Overall Design

This is a non-randomized, single-site, open-label study of the 9vHPV vaccine in 9- to 26-year-old females and males to be conducted in conformance with Good Clinical Practice (GCP).

A total of approximately 200 participants will be enrolled (see Section 5.2). Participants will receive a centrally generated “treatment/randomization number”; however, as all participants will receive the same open-label study vaccine regimen, and no actual randomization will occur. At the time of enrollment, participants must meet all inclusion criteria and must not meet any exclusion criteria.

Collection of medical history and vital signs will be conducted at Day 1 for all participants. Physical examination at Day 1 is optional and will be conducted, per investigator's discretion, if needed to assess inclusion/exclusion criteria.

Study vaccine will be administered under open-label conditions at the following time points: Day 1, Month 2, and Month 6.

Serum samples will be obtained at Day 1 and Month 7 for measurement of anti-HPV antibodies for HPV 6, 11, 16, 18, 31, 33, 45, 52, and 58.

Safety will be monitored from Day 1 until Month 7; a vaccination report card (VRC) will be provided to each participant for recording AE information.

A pregnancy test will be performed on all female participants at Day 1, Month 2, Month 6, and Month 7 visits. Any female participant with a positive pregnancy test at Day 1 will not be vaccinated and will not be allowed to participate in the study. Female participants with a positive pregnancy test after Day 1 will not be vaccinated until after pregnancy outcome. Pregnant participants who receive less than 3 vaccinations during the study will be offered the possibility to complete the vaccination course. Pregnancies and any associated AEs in vaccinated subjects will be followed to outcome.

Specific procedures to be performed during the study, as well as their prescribed times and associated visit windows, are outlined in the Study SoA - Section 2. Details of each procedure are provided in Section 9 – Study Assessments and Procedures.

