9.5.1 Patient Reported Outcome

Adverse events will be documented using a validated VRC.

All participants will receive a VRC at the Day 1, Month 2, and Month 6 study vaccination visits. Using the VRC, the participant or the parent/guardian of the participant will be asked to record the participant's oral temperature in the evening after each study vaccination and daily for 4 days after each study vaccination for the purpose of identifying febrile events. Also, beginning after each study vaccination and for a total of 15 days including the day of vaccination, the participant will be asked to record injection-site and systemic AEs, concomitant medications, and concomitant vaccinations by means of the VRC.

Serious AEs, cancers and overdoses, pregnancy information, lactation information, and infant SAEs will also be collected for the entire duration of the study as described in Section 9.3. In addition, new medical conditions not present at baseline and not reported as an adverse experience will be collected throughout the study.

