10.1 Statistical Analysis Plan Summary

This section contains a brief summary of the statistical analyses for this study. Full details are provided in the following sections.

Study Design Overview	A Phase III open-label, safety, and immunogenicity study of a 9vHPV vaccine administered to 9- to 26-Year-Old Females and Males in Vietnam
Treatment Assignment	Single-arm, open-label, 9vHPV vaccine administration with 1:1 allocation ratio among 9- to 15- and 16- to 26-year-old participants. The study will recruit females and males, with 2:1 enrollment ratio within each age group.
Analysis Populations	Immunogenicity: Per-Protocol Immunogenicity (PPI)
	Safety: All Participants as Treated (APaT)
Primary Endpoint	Percent of participants who seroconverted to HPV Types 6, 11, 16, 18, 31, 33, 45, 52, and 58 at 4 weeks post Dose 3.
Key Secondary Endpoints	Immunogenicity: GMTs of HPV Types 6, 11, 16, 18, 31, 33, 45, 52, and 58 at 4 weeks post Dose 3.
	Safety: Number (and proportion) of participants with the following: vaccine-related SAEs and any SAE (occurring at any time during the study); injection-site AEs, systemic AEs, and discontinuations due to an AE within Day 1 to Day 15 following receipt of 9vHPV vaccination; and, oral temperatures within Day 1 to Day 5 following receipt of 9vHPV vaccination.
Statistical Methods for Key Immunogenicity Analysis	The primary immunogenicity hypothesis will be addressed by calculating point and 95% CI estimates of percent seroconversion based on the exact binomial method of Clopper and Pearson [Clopper, C. J. and Pearson, E. S. 1934].
	The secondary immunogenicity objective will be addressed by calculating point and 95% CI estimates of GMTs based on the t-distribution.
Statistical Methods for Key Safety Analyses	Safety assessments will be descriptive in nature and will include calculation of proportions of participants with adverse events.
Interim Analyses	No interim analyses are planned for this study.
Multiplicity	No multiplicity adjustment is planned as successful demonstration of the primary immunogenicity hypothesis requires the lower limit of the 95% CI of percent seroconversion be >90% of all 9 HPV Types 6, 11, 16, 18, 31, 33, 45, 52, and 58.

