10.4.2 Safety Endpoints

The safety endpoints are the number (and proportions) of participants who reported injection-site AEs, systemic AEs, and discontinuations due to an AE within Day 1 to Day 15 following receipt of 9vHPV vaccination. In addition, SAEs occurring at any time during the study and oral temperatures (reported Day 1 to Day 5 following any vaccination) will be summarized.

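### Section 9.3.1 does not require unrelated, non-fatal SAEs to be reported outside 14 days after each dose, yet the SAP summarises any SAE over the whole study

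*Combined protocol and SAP*

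**What the plan says.** **The reporting duty.** Section 9.3.1 requires full reporting from allocation "through 14 days following the first vaccination(s) and from the time of any subsequent vaccination(s) through 14 days thereafter, all AEs, SAEs" and other reportable events included. It then turns to "any SAE brought to the attention of an investigator at any time outside of the time period specified in the previous paragraph" and makes such an event reportable only in two cases: a death before the participant completes the study, or an SAE the investigator considers vaccine-related.

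**The analysis.** Section 10.1 lists as a safety endpoint "vaccine-related SAEs and any SAE (occurring at any time during the study"). Section 10.4.2 says "SAEs occurring at any time during the study and oral temperatures (reported Day 1 to Day 5 following any vaccination) will be summarized". Section 10.6.2 ends its list of proportions, which includes SAEs, with a Day 1 to Day 15 limit that can be read as covering the whole list or only its last item.

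**Other text on the period.**
- Section 5.1: "Safety will be monitored from Day 1 until Month 7".
- Section 9.5.1: SAEs "will also be collected for the entire duration of the study as described in Section 9.3".
- Table 2: all SAEs are reported in the column headed "Allocation through Protocol-Specified Follow-up Period". In the next column only vaccine-related SAEs remain, together with "any death until participant completion of study". The period that separates the two columns is not defined.

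**The planning figure.** Section 10.9.2 takes 356 of 15,778 earlier vaccinees with an SAE, assumes safety follow-up on all 200 participants, and gives a 99% chance of seeing at least one SAE.

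**The concern.** An unrelated, non-fatal hospitalisation on day 120 falls inside the endpoint of Sections 10.1 and 10.4.2 but outside the duty in 9.3.1. It may well come to light, because safety is reviewed at all four visits. The difficulty is how it is then classified. Section 9.5.1 also collects new conditions that were not reported as adverse experiences, so a site applying 9.3.1 could record the event as new medical history, and it would never enter the SAE count.

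The reported any-SAE proportion would then carry a whole-study label while full reporting was required in only part of the study. Evaluating safety is a secondary objective of a study meant to support licensure in Vietnam, and SAE reports that were never made may not be recoverable at analysis.

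**Working it through.** **1. The plan's own figure.** With p = 356/15,778 = 2.256% and n = 200:

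1 − (1 − p)^200 = 0.9896, with 200p = 4.51 participants expected.

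The 99% reproduces, so there is no calculation error. What is open is whether SAEs in this study are captured as they were in the earlier studies.

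**2. Days under full reporting.** Section 9.1.8 places Dose 1 on the day of allocation. Each window is the vaccination day plus 14 days, so 3 × 15 = 45 days. Follow-up is about 7 × 30 = 210 days, using the plan's 30-day month. The gap is 210 − 45 = 165 days, and the covered share is 45/210 = 0.214.

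- Dose 3 on day 180, Month 7 visit 21 to 49 days later: follow-up ends on day 201 to 229, gap 156 to 184 days.
- Dose 3 anywhere in its ±4-week window (day 152 to 208): follow-up ends on day 152 + 21 = 173 to 208 + 49 = 257, gap 128 to 212 days.

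**3. What the gap could do to the 99%.** The documents do not give the collection window behind 356/15,778. If it matches 9.3.1, the 99% stands. If it covers full follow-up, split the rate by participant:

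- vaccine-related, always reportable: r = 7/15,778 = 0.0444%
- unrelated only: u = 349/15,778 = 2.212%

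Let f be the share of participants with unrelated SAEs who have one inside a window. The documents do not give f, so it is an assumption. The rate captured is r + f·u, and P(at least one) = 1 − (1 − r − f·u)^200.

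| f | Expected participants of 200 | P(at least one SAE) |
|---|---|---|
| 0.214 (even timing, 45/210) | 1.04 | 0.646 |
| 0.50 | 2.30 | 0.901 |
| 0.75 | 3.41 | 0.968 |
| 1.00 | 4.51 | 0.990 |

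Under even timing, P is 0.617 to 0.661 for follow-up of 229 to 201 days, and about 0.58 to 0.71 for 257 to 173 days.

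**4. Break-even.** For P = 0.95 the captured rate must be 1 − 0.05^(1/200) = 1.487%. Then f = (0.01487 − 0.00044)/0.02212 = 0.65.

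The formula does not add back unrelated deaths, which 9.3.1 does make reportable before study completion. It therefore slightly overstates the loss.

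**5. Does Table 2 settle the period?**
- If the follow-up period runs to Month 7, the entry on deaths until study completion has almost nothing left to cover, and the instruction to report all non-serious AEs contradicts the 14-day rule of 9.3.1.
- If it means the 14-day windows, it sits badly with Section 9.3.6, which makes any pregnancy during the trial reportable.

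Neither reading is consistent with the rest of the text.

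**The case against.** The strongest reply is that current text already requires whole-study collection. Section 9.5.1 says so in terms, and its pointer to Section 9.3 could concern the manner of collection only. The opening of 9.3 makes the investigator responsible for detecting and reporting SAEs without naming a window. Appendix 2 has AE and SAE information recorded at each examination. The synopsis says participants are followed to Month 7, which could be taken as Table 2's period. On that view, literal under-reporting is one reading among several.

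This shows that the under-count is not certain; it does not remove the conflict. Section 9.5.1 refers back to a section whose only rule on timing is the narrow one. Appendix 2 governs how events are recorded, not over what period. The synopsis does not define the term in Table 2, and a Month 7 reading creates the difficulties set out in step 5. The heading of 9.3.1 speaks of collecting, so it cannot be set aside as covering expedited reporting only.

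Three points in the reply do stand. The Day 1 to Day 15 phrase in 10.6.2 may attach to its last item alone, so it adds little. The full visit windows give a wider range of gap days than a fixed Month 6 does. The percentages below 99% rest on an assumed f and are illustrations, not estimates.

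**Conclusion.** The concern holds. The reporting rule in 9.3.1 is narrower than the endpoint in 10.1 and 10.4.2, and nothing else in the current text decides between them. The amendment summary records that a whole-study reporting sentence was removed from 9.3.1; that is background, and the conflict lies wholly within the current text.

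The any-SAE proportion may omit unrelated, non-fatal SAEs from about 165 of 210 days. The 99% is correct under full capture, but it is not assured, because its collection window is unstated. If the historical rate covers full follow-up, the chance stays at or above 95% only if about 65% or more of participants with unrelated SAEs have one inside a window. Whether an under-count occurs depends on how the single site reads the text.

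The consequence is limited. Safety analysis is descriptive and the 99% sets no success criterion. This gap does not affect the vaccine-related SAE endpoint in Section 4, the 7.7%, or the upper bound of 1.8%, because vaccine-related SAEs are reportable at any time. It should be fixed, but it does not threaten the primary hypothesis.

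**What to change.** Reconcile the passages in one of two ways.

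(a) **Collect for the whole study.** Make 9.3.1 and Table 2 require all SAEs, whatever their cause, from allocation through the Month 7 contact. Define Table 2's follow-up period for SAEs accordingly, while keeping the 14-day rule for non-serious AEs distinct. State in 10.6.2 that SAEs and vaccine-related SAEs are summarised from Day 1 to Month 7.

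(b) **Keep the 14-day rule.** Redefine the endpoint in 10.1 and 10.4.2 as SAEs on Day 1 to Day 15 after any dose, plus deaths and vaccine-related SAEs at any time during the study. Align 9.5.1, and restate the 99% in 10.9.2 with the window it assumes.

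Either is a wording amendment, with no change to visits or sample size. Under even timing, (a) adds SAE reports for about 200 × 0.02212 × (1 − 0.214) = 3.5 participants at one site, from visits where safety is already reviewed. Option (b) gives up a whole-study any-SAE proportion. Option (a) preserves the endpoint that the SAP already states.
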